1. OBJECTIVES

The objective of this study is to assess whether there is activity of MBG-453, a humanized monoclonal antibody targeting TIM-3, in the treatment of patients with lower-risk MDS.

1.1 Study Design

This is an adaptive two-stage phase II clinical trial to assess the activity of the anti-TIM-3 antibody, MBG453, in patients with lower-risk MDS, not eligible for or progressing on frontline therapy. We will evaluate the overall response rate (ORR) using international working group criteria. Patients will receive MBG453 dosed at the recommended phase II dose of 800mg and administered on day 1 of a 28 day cycle.

In this study, we seek to test MBG453 monotherapy in patients with lower-risk MDS unresponsive to or progressive after standard initial therapy. We will include patients progressing on prior ESA therapy or those that have an EPO level > 500, as well as patients with MDS who have cytopenias that require treatment and who are not felt to be candidates for or lack other treatment options.

This is an adaptive two-stage Phase II trial. We will plan to treat patients with MBG453 on day 1 of a 28 day cycle. Patients will be treated with MBG453 dosed at 800mg every 28 days. AEs will be assessed, with particular attention paid to monitoring for immune mediated adverse events. The primary endpoint, ORR, will be assessed as the best response within the first 6 months of treatment. Patients may stay on treatment until progression. The study will assume a historical null response rate of 0.15 (e.g. based on MEDALIST) and will be powered to detect an ORR of 0.35 with MBG453.

Simon's two-stage design (Simon, 1989) will be used. The null hypothesis that the true response rate is 0.15 will be tested against a one-sided alternative. In the first stage, 10 patients will be accrued. If there are no more than 1 responses in these 10 patients, the study will be stopped. Otherwise, 12 additional patients will be accrued for a total of 22. The null hypothesis will be rejected if 6 or more responses are observed in 22 patients. This design yields a type I error rate of 0.09 and power of 0.80 when the true response rate is 0.35.

The study will collect adverse events during the first 28 days of treatment for the first 6 patients treated on study to assess for dose-limiting toxicities (DLTs). DLTs will be defined as grade 3 or higher non-hematologic toxicities that are possibly, probably, or definitely related to the study drug (see section 5.4 for more detail). Low blood counts will not be considered DLTs; however, in the setting of persistent grade 4 cytopenias thought possibly, probably, or definitely related, and not resolving within 14 days, a bone marrow is recommended. If the bone marrow is absent of disease then this would be considered a DLT. If more than one of the first six patients enrolled experiences a DLT, enrollment will stop and safety will be assessed for this population prior to further enrollment.

Serious adverse events (SAEs) will be monitored; these preliminarily include deaths, life-threatening AEs, hospitalization, birth defects, or important medical events. SAEs should undergo expedited reporting to the IRB/FDA and Novartis, as appropriate. Patients will be followed for

survival up to 12 months after stopping MBG453

1.1 Primary Objectives

- The primary objective of this study is to evaluate the overall response rate (ORR) within first 6 months of treatment of MBG453 in patients with lower-risk MDS

1.2 Secondary Objectives

- To assess rates and severity of adverse events associated with MBG453 in lower risk MDS
- To evaluate rates of 1-year overall survival (OS), progression free survival (PFS), time to disease progression, and duration of response to therapy with MBG453.
- To characterize the response to therapy according to pretreatment disease and patient characteristics, monitoring disease-specific molecular, immunophenotypic, and cytogenetic evolution during treatment (exploratory analysis).
- To describe changes in cell surface marker expression, Immune cell subsets, and molecular clonal evolution during treatment and at the time of progression (exploratory analysis).

2. BACKGROUND

2.1 Study Disease(s)

Myelodysplastic syndromes (MDS) comprise a spectrum of advanced hematologic malignancies characterized by ineffective clonal hematopoiesis and the risk of progression to acute myeloid leukemia. Patient disease risk is characterized according to the presence and depth of cytopenias, recurrent cytogenetic abnormalities, and the number of blasts, typically using the IPSS or IPSS-R risk scores (Greenberg et al Blood 1997, 2012). In general, patients are divided into “lower-risk” and “higher-risk” disease based on overall survival and AML progression; patients with higher-risk disease generally proceed to disease modifying therapy with hypomethylating agents or transplant, while those with lower-risk disease generally receive symptom-directed therapy, most commonly toward RBC transfusion needs but also for thrombocytopenia and neutropenia.

The most commonly employed therapy for patients with lower-risk MDS is erythropoiesis stimulating agent (ESA) therapy, using epoetin alfa or darbepoetin alfa (Davidoff et al, Leuk Res 2013). These agents may alleviate red blood cell (RBC) transfusion requirements in 40-60% of patients, and a number of variables may predict for a higher chance of response, including a serum erythropoietin level < 100 IU/mL, limited prior transfusion history, and having lower-risk disease. Unfortunately, many patients will have limited responses to ESAs, have features such as an EPO level > 500 IU/mL and be unlikely to respond, or become transfusion dependent again after an initial response (Buckstein et al Am J Hematol 2017). These patients represent a significant unmet clinical need; although their MDS may not progress or transform for years, transfusion dependence is a significant burden on quality of life and can result in complications including iron overload and the formation of antibodies to blood products. For patients with thrombocytopenia or neutropenia, isolated or associated with anemia, therapies are lacking, and they may trial immunosuppressive agents or hypomethylating agents, but currently there is no standard of care. Such cytopenias are associated with bleeding complications or recurrent infectious complications.

New approaches to transfusion dependence and symptomatic cytopenias in lower-risk MDS are desperately needed. Historically, rates of blood count improvement are low without treatment; in the recent MEDALIST trial (Fenaux et al., 2020), which compared therapy with luspatercept to supportive care alone (placebo), 13% of patients receiving placebo achieved the primary endpoint, and this serves as a historical comparator in identifying new active compounds.

Currently, the only curative therapy for MDS is allogeneic transplant; the mechanism by which allogeneic transplant is effective in MDS is thought to be immune mediated through graft vs. leukemia effect, particularly when using a reduced intensity conditioning regimen (Weisdorf et al., 2012). Even in the absence of allogeneic transplantation, immune checkpoint dysregulation may contribute to disease progression for patients with MDS, CMML, and AML (Aggarwal et al., 2011). T-cell immunoglobulin and mucin domain containing molecule-3 (TIM-3) which is expressed on T-cells as well as on leukemic stem cells in MDS (Asayama et al., 2015; Kikushige et al., 2014, 2010; Tao et al., 2014). Interestingly, while TIM-3 is aberrantly expressed on leukemic blasts, it does not appear to be present on normal hematopoietic stem cells. TIM-3 is expressed on T-cells and plays a role in immune checkpoint control; upon encountering galectin-9 on tumor cells, TIM-3 is phosphorylated and downregulates the T-cell response against the tumor.

2.2 IND Agent: MBG453

MBG453 is a humanized monoclonal antibody targeting TIM-3, and acts as an immune checkpoint inhibitor. TIM-3 may have activity as monotherapy and in conjunction with hypomethylating agent treatment in MDS, both due to direct activity against leukemic stem cells, as well as enhancement of immune response toward myelodysplastic cells. Previous studies have explored TIM3 inhibition with MBG453 in MDS and AML (NCT03066648) but to date it has not been explored in lower-risk disease.

MBG453 is a humanized IgG4 antibody which interferes with the binding site of phosphatidylserine to the TIM-3 receptor. Primate studies were performed to assess PK and tolerability; doses of 10mg/kg to 100mg/kg administered intravenously each week showed safe administration with transient declines in CD4+ and CD8+ T cells, and monocytes. No other toxicity was noted. MGB453 was also studied for its potential to induce cytokine release in human donor blood *in vitro*; these studies, compared to an IgG4 isotype control and positive control antibodies, did not show an effect on cytokine release.

MBG453 was evaluated in patients with solid tumors; as of July 2019 252 patients had been treated with MBG453 as monotherapy or in combination with an anti-PD1 IgG4 antibody in a first in human clinical trial for patients with solid tumors, 133 of which received it as monotherapy. PK parameters demonstrate dose-proportional increases in exposure between 80mg and 1200mg, with moderate accumulation using either every 2 week or every 4 week dosing. No DLTs were observed with MBG453 monotherapy. Among patients treated with MNG453 in combination with the anti-PD1 antibody PDR001, PK data for MBG453 appeared comparable to monotherapy; one DLT of myasthenia gravis was reported in a patient with thymoma treated at a dose of 240mg MBG453 + 80mg PDR001 every 4 weeks.

MBG453 has also been studied in hematologic malignancies, specifically in patients with AML or MDS. A total of 152 patients were treated as of July 2019; 26 patients received MBG453 as monotherapy, while others received it in combination with decitabine, azacitidine, and/or PDR001. There were similar PK data as seen in the solid tumor study. Four patients treated with MBG453 in combination with decitabine experienced DLTs during the first 2 cycles which included Grade 3 hepatitis (Arm 2: MBG453 240 mg Q2W + Decitabine 20 mg/m²), Grade 3 tubulointerstitial nephritis (Arm 3: PDR001 400 mg Q4W + MBG453 160 mg Q2W + Decitabine 20 mg/m²), Grade 3 encephalitis (Arm 5: PDR001 400 mg Q4W + MBG453 240 mg Q2W) and Grade 2 uveitis (Arm 3: PDR001 400 mg Q4W + MBG453 400 mg Q2W + Decitabine 20 mg/m²).

Of the 26 patients with MDS or AML treated with MBG453 as a single agent, 24 patients (92%) experienced AEs of any grade, regardless of relationship to study drug, with the most frequent AEs (>10%) being abdominal pain and febrile neutropenia (6 patients each, 23%), constipation, decreased appetite, diarrhea, dyspnea, nausea and pyrexia (5 patients each, 19%), dizziness, peripheral edema, and platelet count decreased (4 patients each, 15%), anemia, fatigue, headache, pain and pneumonia (3 patients each, 12%). A total of 17 patients (65%) experienced SAEs of all grades, regardless of relationship to study drug. SAEs which occurred in more than one patient included febrile neutropenia (6 patients, 23%), pneumonia and pyrexia (3 patients each, 12%). A total of 10 patients experienced a grade 3 or higher AE possibly related to the study drug: hypertension (n=2), neutropenia (n=2), thrombocytopenia (n=4), rash (n=2).

Potential immune mediated toxicities have been monitored with MBG453. Approximately 6-15% of patients have experienced skin-related AEs, the majority being grade 1 or 2 and reversible. A total of three patients with grade 3 rashes have been reported across both the solid tumor study and the MDS/AML study to date. Hepatic AEs have also been observed; these have predominately been AST or ALT elevations, typically grade 1-2; no bilirubin increase has been noted. Periodic monitoring of liver enzymes is required. In the MBG453 study evaluating MDS and AML several possible immune-related toxicities were noted: one patient with myositis with MBG monotherapy. When combined with the PD1 inhibitor PDR001, one case of tubulointerstitial nephritis was noted and two cases of encephalitis. In combination with decitabine, one case each was noted for inflammatory arthritis, pericarditis, stomatitis, and one possible hemophagocytic lymphohistiocytosis that was possibly immune related and in the setting of active disease.

For complete information, please refer to the current Investigator's Brochure: MBG453 Investigator's Brochure, Edition 5.1, Release Date 11-Dec-2019.

2.3 Rationale

T-cell immunoglobulin and mucin domain containing molecule-3 (TIM-3) is expressed on T-cells as well as on leukemic stem cells in MDS (Asayama et al., 2015; Kikushige et al., 2014, 2010; Tao et al., 2014). TIM-3 has been characterized as an immune checkpoint in that it is a negative regulator of T-cell immunity, and is overexpressed on immune cells in cancer samples. TIM-3 expressed on T-cells plays a role in immune checkpoint control; upon encountering galectin-9 on

tumor cells, TIM-3 is phosphorylated and downregulates the T-cell response against the tumor. TIM-3 appears to be co-expressed with PD-1 and represent T-cell exhaustion; it is proposed as a possible mechanism of escape from immune checkpoint blockade (Anderson et al., 2016; Datar et al., 2019).

TIM-3 expression can be found on a number of hematologic cells, including monocytes and NK cells, and may be involved in regulating the inflammatory response (da Silva et al., 2014; Leavy, 2008). Further studies have identified TIM-3 expression on leukemic blasts; TIM-3 expression appears to be aberrantly increased on malignant leukemic blasts and not present on normal hematopoietic stem cells (Jan et al., 2011). In a murine xenograft model of serial transplantation of AML cells, administering an anti-TIM-3 antibody resulted in blocked engraftment, suggesting that TIM-3 inhibition may target leukemic precursors directly (Kikushige et al., 2010). The exact signaling mechanism of TIM-3 in leukemic precursors is under investigation.

In the previous study of MBG453 monotherapy for patients with relapsed and refractory AML or MDS, a number of patients exhibited hematologic responses (Borate, 2019), including decreased RBC transfusion needs and improvement in platelet and neutrophil counts. Several patients exhibited sustained blood count responses after multiple prior lines of treatment for refractory disease, suggesting that there may be a role of TIM-3 inhibition in hematopoiesis (Figure 1).

Figure 1. Example of a hematologic response seen in a patient on MBG453 monotherapy. The patient experienced neutrophil and platelet recovery.

Given the evidence of blood count responses in patients with advanced myeloid disease, and the favorable toxicity profile of MBG453 monotherapy, there is rationale to study MBG453 monotherapy for the treatment of lower-risk MDS. For those patients who are RBC transfusion dependent, they must have progressed after ESA therapy or be unlikely to respond to ESA therapy,

characterized by an EPO level >500, who are not felt to be candidates for or lack other treatment options. In addition, given early activity, there is particular interest in neutrophil and platelet responses to MBG453. These remain significant complications of MDS, with infectious and bleeding events identified as common causes of death from MDS. Therefore, patients with lower-risk MDS characterized by other cytopenias are also eligible if they require therapy, have cytopenias that can be assessed for IWG response, and are not eligible for or have progressed on other standard therapy.

2.4 Correlative Studies Background

Throughout the study, at designated time points, patient blood and marrow samples will be collected for correlative analysis. Specifically, we will viably cryopreserve peripheral blood and bone marrow samples serially at baseline, during treatment, and at the end of treatment/time of progression. We will collect blood samples just prior to each infusion of MBG453 during cycles 1-3, and a bone marrow assessment will be performed at baseline, after cycle 2, after cycle 4, and then per the treating investigator. Peripheral blood and bone marrow samples will be collected at end of treatment or progression.

We propose correlative studies to better characterize the effect of TIM3 inhibition on the MDS progenitor cells as well as T-cell subsets. We have previously developed a mass cytometry panel that assesses peripheral blood T-cells, myeloid components, and bone marrow cells with specific attention to markers relevant to MDS and immune checkpoint targets (Preliminary Markers, Table 1).

Immune Monitoring Panel	Tumor/LSC Marker Panel
CD3, CD4, CD8, CD11b, CD11c, CD14, CD16, CD19, CD20, CD25, CD27 CD28, CD38, CD44, CD45, CD45RA, CD45RO, CD56, CD57, CD62L, CD95 (Fas), CD123, CD127, CD134 (Ox40), CD137 (41BB), CD152 (CTLA4), CD161, CD195 (CCR5), CD197 (CCR7), CD223 (LAG3), CD278 (ICOS), CD279 (PD-1), CD366 (TIM3), HLA-DR	CD3, CD7, CD11b, CD11c, CD14, CD15, CD16, CD19, CD33, CD34, CD38 CD44, CD45, CD64, CD99, CD117, CD123, CD135, CD163, CD184, CD206, CD366 (TIM3), CD371, HLA-DR

The primary aim of this correlative will be to use mass cytometry to better characterize in-patient changes in T-cell and myeloid cell populations during treatment with MBG453. This work will be done in coordination with the laboratory of [name] (MGH Vaccine and Immunotherapy Center).

We will also perform serial NGS myeloid somatic mutation testing to characterize subclonal MDS changes during treatment. We will use these correlatives studies to explore the biological response to this drug combination including emerging mutations as putative escape mechanisms. We will collect standard tumor characteristics including tumor subtype, cytogenetics, cell surface markers, molecular abnormalities, both at study entry and during treatment. We will analyze whether certain

MDS characteristics are associated with a specific response to therapy or change in cell populations.

3. PARTICIPANT SELECTION

The purpose of this study will be to evaluate the activity of MBG453 in the treatment of patients with lower-risk MDS.

3.1 Eligibility Criteria

3.1.1 Lower risk MDS patients (IPSS-R score ≤ 3.5 at diagnosis) who have progressed or are refractory to/intolerant of prior therapy and meet one of the following categories:

- RBC transfusion dependent according to IWG criteria must either be unresponsive to prior ESA therapy or have an EPO level > 500
- Prior HMA therapy
- Patients with the following cytopenias who otherwise are felt to require treatment per the treating physician:
 - Platelets $< 50k/uL$
 - ANC < 500 cells/uL
- Patients with MDS with isolated del(5q) (“5q- syndrome”) must have progressed on or not tolerated lenalidomide
- Patients who are not felt to be candidates for or lack other standard treatment options. Patients with prior luspatercept exposure are eligible.
- Patients with dysplastic type CMML (WBC $< 13,000$ cells/uL) meeting the above criteria are eligible; responses will be assessed using MDS criteria

3.1.2 Age ≥ 18 years. Because no dosing or adverse event data are currently available on the use of MGB453 in participants < 18 years of age, children are excluded from this study, but will be eligible for future pediatric trials.

3.1.3 ECOG performance status ≤ 2 (see Appendix A).

3.1.4 Participants must have adequate organ and marrow function as defined below within 21 days of treatment:

- Total bilirubin ≤ 2 mg/dL (unless due to Gilbert’s in which case it must be < 3 mg/dL)
- AST(SGOT)/ALT(SGPT) $\leq 3 \times$ institutional ULN
- Creatinine clearance ≥ 30 mL/min/1.73 m² (by MDRD calculation)

3.1.5 Human immunodeficiency virus (HIV)-infected participants on effective anti-retroviral therapy with undetectable viral load over the prior 6 months are eligible for this trial.

3.1.6 Participants with known history or current symptoms of cardiac disease, or history of treatment with cardiotoxic agents, should have a clinical risk assessment of cardiac function using the New York Heart Association Functional Classification. To be eligible

for this trial, participants should be class 2B or better.

3.1.7 Ability to understand and the willingness to sign a written informed consent document.

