3.2 Exclusion Criteria

3.2.1 Participants who have had chemotherapy or radiotherapy within 14 days or five half-lives, whichever is shorter, prior to the first dose of study treatment.

3.2.2 Participants who are receiving any other investigational agents; a washout of 14 days or 5 half-lives, whichever is longer, is required. The washout period for biologic agents should be 28 days since the last dose.

3.2.3 Prior exposure to a TIM-3 inhibitor.

3.2.4 Active autoimmune disease requiring > 10 mg per day of prednisone or the equivalent. Inactive or controlled autoimmune disease is allowed.

3.2.5 Prior solid organ transplant is exclusionary. Patients with prior hematopoietic cell transplant are eligible if they are over 6 months from transplant and not on any related immunosuppressive therapy.

3.2.6 History of allergic reactions attributed to compounds of similar chemical or biologic composition to MBG453.

3.2.7 Active untreated or concurrent malignancy that is distinct in primary site or histology, excluding:

- The following will not be exclusionary: non-melanoma skin cancer, noninvasive colonic polyps, superficial bladder tumors, cervical cancer in-situ, ductal carcinoma in situ of the breast, monoclonal B-cell lymphocytosis, or monoclonal gammopathy of undetermined significance.
- Hormonal therapy is allowed.
- History of other malignancy is allowed if not requiring active management.
- Other malignancies that were treated with curative intent at least 1 year prior to study screening and without evidence of active disease will be allowed.
- Participants with a prior or concurrent malignancy whose natural history or treatment does not have the potential to interfere with the safety or efficacy assessment of the investigational regimen are eligible for this trial pending discussion with the principal investigator.

3.2.8 Participants with uncontrolled intercurrent illness.

3.2.9 Participants must not have clinically active HBV or HCV; testing is not required

3.2.10 Receipt of a live vaccination within 28 days of cycle 1 day 1

3.2.11 Participants with psychiatric illness/social situations that would limit compliance with study requirements.

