5.2. Pre-Treatment Criteria

5.2.1. Cycle 1, Day 1

Patients should have C1D1 labs that meet inclusion criteria and otherwise be clinically stable per the treating investigator, prior to starting treatment on C1D1. These labs include total bilirubin, creatinine, and ALT/AST (Section 3.1.4).

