9.1.2. Correlative Study 2: Exploring genetic factors associated with response and progression

Background: We will perform serial NGS-based testing for recurrent myeloid somatic mutations to characterize subclonal MDS changes during treatment. We will use these data to explore the biological response to MBG453 including mutations that confer sensitivity to treatment, and emerging mutations as putative escape mechanisms. We will collect standard tumor characteristics including tumor subtype, cytogenetics, cell surface markers, molecular abnormalities, both at study entry and during treatment. We will analyze whether certain MDS characteristics are associated with a specific response to therapy or change in cell populations. NGS-based testing will be performed per local institutional standards at with bone marrow biopsies at Baseline, C3D1, and End of Treatment (EOT). In the event of a dry tap, peripheral blood may be substituted.

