
a: Albumin, alkaline phosphatase, total bilirubin, direct bilirubin, bicarbonate or CO₂, BUN, calcium, chloride, creatinine, glucose, LDH, phosphorus, potassium, magnesium, total protein, SGOT [AST], SGPT [ALT], sodium, uric acid, amylase, lipase.
 
b: Serum pregnancy test (women of childbearing potential, WOCP). At screening, a serum pregnancy test (serum β-HCG) must be performed within 3 days before the first dose for WOCP. During the study, a urine / serum pregnancy test should be done at Day 1 of each cycle for WOCP (except Cycle 1 if a pregnancy test had been performed within 72 hours of the first dose) and at EOT visit. A pregnancy test (serum or urine) should be performed every month during the safety follow-up period for WOCP (until day 150). If the patient is not coming to the clinic during the safety follow-up, it can be performed at home or at a local doctor's office, and the results will be communicated to the site staff.
 
c: Bone marrow biopsy and aspirate should be performed at baseline, cycle 3 day 1 ±3 days, and then within 7 days of cycle 5 day 1, at end of treatment, and as clinically indicated. Standard institutional testing including cytogenetics and molecular testing is recommended.
 
d: Off-treatment evaluation. The in-person visit has a window of ±3 days; additional safety follow-up is required through day 150. Note: for IND/IDE trials, follow up visits or other contact are required in order to identify SAEs during the 30 days following the end of study treatment. After end of treatment visit, patients should be followed per section 5.7 for survival and progression.
 
e: Bone marrow assessment for cycle 7 and cycle 11 may be done up to 7 days prior to the start of the treatment cycle. If a patient has a bone marrow assessment within 1 cycle of the planned assessment (e.g. cycle 6 or cycle 10) this may be used for the study assessment. A bone marrow for research samples will be performed on cycle 1 day 3 (window day 3-6).
 
f: Bone marrow samples for correlative studies will be collected at baseline, at cycle 3 day 1, and EOT for both NGS testing and for cytof analysis.
 
g: Blood pressure, heart rate, and temperature will be performed at screening and then as clinically indicated. . Bone marrow biopsy on cycle 5 day 1 will only require Cytof samples to be obtained.
 
h: On C1D1, total bilirubin, direct bilirubin, creatinine, SGOT [AST], SGPT [ALT], and INR should continue to meet inclusion criteria. Baseline values will be those assessed on C1D1
 
i: Follow up to evaluate for progression and survival may be ±7 days from those noted (day 30, 150, 250, and 1 year). Safety evaluations must be through 150 days after the last dose of MBG453. The safety follow up can be done by telephone call or visit. The information collected is kept as source documentation. All SAEs reported during this time period must be reported as described in Section 7.3. Documentation of attempts to contact the subject should be recorded in the source documentation.
 
j: TSH, free T3, and free T4 should be obtained during screening. TSH should be monitored regularly (at selected visits) during treatment and as clinically indicated. If TSH is abnormal, then test free-T3 and free-T4.
 
k: Rapid Heme Panel for NGS should be collected as part of standard of care with bone marrow biopsies at screening, C3D1 (+/-3 days), and EOT/progression. In the event of a dry tap, peripheral blood may be substituted.
											

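### Does scoring lower-risk MDS at diagnosis, with entry cytogenetics only recommended in the calendar, call for a change to the plan?

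*Combined protocol and SAP*

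**What the plan says.** Section 3.1.1 defines the population as "Lower risk MDS patients (IPSS-R score ≤ 3.5 at diagnosis) who have progressed or are refractory to/intolerant of prior therapy". Prior HMA treatment is one of the qualifying categories, and section 3.2.5 adds that "Patients with prior hematopoietic cell transplant are eligible if they are over 6 months from transplant", provided they take no related immunosuppression. Neither 3.1 nor 3.2 sets a blast limit at entry. The day 1 check in 5.2.1 concerns organ function ("These labs include total bilirubin, creatinine, and ALT/AST") and clinical stability in the investigator's judgement.

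On what makes up risk, section 2.1 says: "Patient disease risk is characterized according to the presence and depth of cytopenias, recurrent cytogenetic abnormalities, and the number of blasts". It also says that "patients with higher-risk disease generally proceed to disease modifying therapy with hypomethylating agents or transplant", and that lower-risk patients with low platelets or neutrophils may try an HMA.

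On cytogenetics at entry, section 9.1.2 says "We will collect standard tumor characteristics including tumor subtype, cytogenetics, cell surface markers, molecular abnormalities, both at study entry and during treatment", and section 2.4 says the same. Both then state that associations between MDS characteristics and response will be analysed. The calendar in section 10 schedules a marrow at screening, with an EDC timepoint and footnote c, which says "Standard institutional testing including cytogenetics and molecular testing is recommended". Sequencing has its own row and footnote k: "Rapid Heme Panel for NGS should be collected as part of standard of care with bone marrow biopsies at screening".

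On reporting, section 13.1 lists response by pretreatment disease and patient characteristics as exploratory and names no variable. Section 13.3 names prior HMA and prior TGF-beta agents. The primary test stops at 1 or fewer responses in 10 and rejects at 6 or more in 22.

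**The concern.** The objective is stated for lower-risk MDS, but the score is dated at diagnosis and the patients have since progressed or exhausted prior therapy. Some may have moved to higher risk by entry, and no eligibility or day 1 criterion would detect it. If those patients respond differently, the ORR describes a mixture.

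A reader might then want the responders classified by risk at entry. That needs blasts, cytopenias and karyotype. The first two are scheduled. The third is promised in the correlative sections but only recommended in the calendar, so a site could skip it without a deviation. A karyotype not obtained at screening cannot be recovered later, and the cytogenetic response of section 11.1 and the cytogenetic evolution of section 13.1 would lack a baseline for that patient. Section 13 names neither IPSS-R nor blasts at entry, nor prior transplant, as a reporting variable.

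The threshold of 6 in 22 sharpens this, because a positive result may rest on one or two responders.

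**Working it through.** **1. The plan's own figures.** Inputs from section 13.1: 10 then 12 patients, stop at 1 or fewer, reject at 6 or more of 22, rates 0.15 and 0.35. With X1 ~ Bin(10, p) and X2 ~ Bin(12, p),

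P(reject) = Σ (x = 2 to 10) P(X1 = x) · P(X2 ≥ 6 − x).

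This gives 0.0907 at p = 0.15 and 0.8040 at p = 0.35, reproducing the stated 0.09 and 0.80. At p = 0.25 it gives 0.4505.

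**2. How often rejection rests on 6 or 7 responses.**

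| True ORR | P(reject) | P(6 or 7, rejecting) | Share of rejections |
|---|---|---|---|
| 0.15 | 0.091 | 0.080 | 0.080/0.091 = 88% |
| 0.25 | 0.451 | 0.292 | 0.292/0.451 = 65% |
| 0.35 | 0.804 | 0.284 | 0.284/0.804 = 35% |

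The 88% is conditional on an event with probability 0.09. The concentration comes from the threshold and the sample size, and has nothing to do with how risk is scored. It would argue equally for listing responders by any baseline variable.

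**3. What changed risk could do to the test.** The documents give neither the share f of patients who are no longer lower-risk nor their response rate, so both are assumed here. The mixed rate is p = (1 − f) · (lower-risk rate) + f · (other rate), put into the formula above.

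| Lower-risk rate | Other rate | f | p | P(reject) |
|---|---|---|---|---|
| 0.35 | 0.15 | 0.1 | 0.33 | 0.75 |
| 0.35 | 0.10 | 0.2 | 0.30 | 0.65 |
| 0.35 | 0.05 | 0.3 | 0.26 | 0.49 |
| 0.15 | 0.35 | 0.1 to 0.3 | 0.17 to 0.21 | 0.14 to 0.28 |
| 0.15 | 0.05 | 0.1 to 0.3 | 0.14 to 0.12 | 0.07 to 0.04 |

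The effect runs in either direction and vanishes if the rates are equal. A table by risk at entry would leave every row as it is.

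**4. What such a table could show.** If 4 of 22 patients scored above 3.5 at entry (assumed), the exact 95% interval for that share is 0.05 to 0.40. One response among those 4 gives 0.01 to 0.81. It could describe, but not separate the groups.

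**5. The cytogenetics texts side by side.** Sections 2.4 and 9.1.2 speak of collecting standard characteristics. Footnote c, attached to the screening marrow, speaks of standard institutional testing. They can be read together: the study records what the institution's standard work-up yields. Footnote c uses the same verb for molecular testing, which has its own calendar row, so the verb alone does not mark a test as optional.

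**6. What a missing screening karyotype would cost.** An IPSS-R at diagnosis presupposes a karyotype at diagnosis, given the inputs in section 2.1. Screening blasts and blood counts update the other inputs. Only a change in karyotype since diagnosis would be missed, and only where screening cytogenetics was not done. Section 11.1 presents cytogenetic response as something that may be assessed in addition, outside the ORR.

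**The case for a change.** The strongest case for acting is that the mismatch is real and cheap to remove. Two sections promise data that the calendar does not require, and a screening karyotype not obtained is lost. Naming blasts and IPSS-R at entry before results are known would also limit selective choice among many characteristics in 22 patients.

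The first part stands as a point of wording. It touches exploratory cytogenetic evolution and an optional response measure, and no stated conclusion depends on either. The second is a preference about detail within an analysis already planned and labelled exploratory. With at most 22 patients, an analyst asked for response by pretreatment disease characteristics would naturally consider blasts and risk score. Prior transplant can be tabulated in the same way.

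The obvious categories for blasts need care as well. The bands in section 11.1 were written for progression, and 5-10% and 10-20% both contain 10%.

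That the trial may enrol patients whose risk has changed also stands as a fact. But the protocol fixes its population at diagnosis and deliberately admits patients who have progressed since. To call them outside the target is to apply a different definition.

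**Conclusion.** The concern does not call for a change. Dating risk at diagnosis is an explicit choice of population, and the primary analysis population, test and decision rule would be the same with or without the extra tables. The design's stated 0.09 and 0.80 reproduce as 0.091 and 0.804. The possible shift in rejection probability (power down to 0.49 at worst, or null rejection up to 0.28, among the scenarios shown) rests wholly on assumed shares of 10% to 30% and assumed response rates, and reporting cannot reduce it.

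The difference between collecting cytogenetics and recommending it is a minor wording mismatch that the study team can resolve when setting up data collection. This conclusion assumes that the screening marrow and blood count are done as scheduled, so that blasts and cytopenias at entry are on record, and that the planned exploratory analysis is reported descriptively. It also takes the trial's claim to concern patients who were lower-risk at diagnosis; a claim about patients confirmed lower-risk at entry would need more than the plan provides.
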